5.10 Device Training

Full training on all aspects of the study will be provided by the Sponsor as follows:

- Identification of teeth according to ICDAS caries coding system
- Tooth cleaning protocol
- Full preparation and use of the Calcivis Sytem according to the manufacturer's Instructions For Use, to include –
 - preparation of the disclosing solution, syringe loading and device activation
 - laptop set-up, image interpretation and storage
- Informed Consent procedures, study procedures and data recording
- Adverse event collection, recording and reporting

All training will be fully documented for Investigators / Orthodontists and Dental Nurses. In addition technical support will be available on the study visit days, if required.

6. RISKS AND BENEFITS

6.1 Risk Analysis

Extensive risk analyses have highlighted the following potential areas of safety concern (high impact risks):

1. Integrity of the single use Applicators
2. Deterioration of the Disclosing Solution throughout its shelf life
3. Toxicity of the Disclosing Solution
4. Contamination of vial from re-use (multi-use format only)

These are all considered very low likelihood and have all been adequately addressed by:

1. Integrity testing of applicators in addition to breach requiring a triple fault condition in that previous patient would need to be carrying disease, main device would have to not be cleaned between uses and any contaminant on device would need to penetrate to subsequent patients.
2. Extensive stability studies on the Disclosing Solution
3. Extensive pre-clinical toxicological study and recent clinical study on Disclosing Solution shows no sign of toxicity
4. The multi-use reconstituted solution contains an anti-microbial preservative. In addition , wiping top of Photoprotein vial with alcohol wipes between uses and drawing up of photoprotein with single-use syringes.

6.2 Potential Risks

The Calcivis system has been designed and tested in compliance with ISO 13485 and will only be used by fully trained dental professionals. Any risks associated with the use of the Calcivis System have been analysed as above, and provision made to either reduce or eliminate these risks. Potential risks to the patient include:

- cross-contamination between patients, if not used according to manufacturer's instructions
- hypersensitivity of patient to protein or other components in Disclosing Solution
- over / under application of Disclosing Solution leading to necessity for repeat procedure
- discomfort and / or soft tissue trauma due to presence of intra-oral imaging device in mouth

6.3 Potential Benefits

This study is intended to evaluate the Calcivis System for monitoring lesion activity behaviour in orthodontic patients by evaluating active demineralization on tooth surfaces over time, in a clinical setting. When used to characterise and monitor de-mineralization in teeth, it is anticipated that the Calcivis System will benefit both the user (dentist) and patient. Potential benefits to the patient are:

- treatment of early lesions with re-mineralization therapies or sealants to prevent progression to cavitation
- enhanced clinical decision making
- reducing the need for X-rays

- improved communication between dentist and patients and improved potential for prevention of caries

It is therefore anticipated that the overall benefits will outweigh any risks associated with the use of the Calcivis System.

7. STUDY DESIGN

7.1 Overview

This is a prospective, single-site, non-randomised, post-approval clinical study to assess the use of the Calcivis System for monitoring the activity levels of post-orthodontic treatment white spot caries lesions over time, from baseline (de-bond) to 8 weeks post de-bond.

This post-approval clinical study will be conducted under the controlled conditions of this clinical study plan, on eligible patients in a clinical setting (NHS hospital, orthodontic clinic), by three Investigators.

7.2 Patient Selection and Confidentiality

Patients will be recruited to the study from an NHS hospital, orthodontic clinic. Patients will initially be identified and selected according to Inclusion Criteria and the Exclusion Criteria listed below from those attending for orthodontic treatment and who are ready for de-bond. Patients must provide written informed consent (or parents or guardians where the patient is not competent to provide written informed Consent), and be willing to adhere to the study schedule, before being entered in to the study, however, only patients who have 'active' lesions on de-bond, as confirmed with the Calcivis System at the baseline visit, will be followed up in this study. If all lesions are assessed as 'inactive', the patient will be withdrawn from the study.

It is expected that up to 100 patients may have to be recruited and imaged with the Calcivis System at de-bond (baseline), in order to find 45 patients with active lesions.

Patients will be encouraged to complete all Study Visits, however, patients are free to withdraw Consent at any time, irrespective of their initial consent. Patients may also be withdrawn from the study by the Investigator on the grounds of safety. Any patients who withdraw or are withdrawn from the study will be replaced.

All patients recruited to the study will be identified by a unique study number, comprising the site number and a patient number, to allow any data collected on them to be anonymised. The investigator will maintain a confidential patient identification list of all patients enrolled in the study (by name and patient number). The list will be maintained at the site and will not be retrieved by the Sponsor.

Only patients with 'active' lesions will be followed up in this study, therefore no randomization will be required.

7.3 Study Duration

The overall study period is expected to take 18 months - 3 months for Ethics Committee and NHS, R & D approvals, 12 months for recruitment and study procedures, and 3 months for final follow up, data collection and analysis.

7.4 Inclusion and Exclusion criteria

Inclusion criteria

1. Patient must be ≥ 12 years old
2. Patient must have had orthodontic appliances placed on the upper incisors and canines for at least 12 months, and be ready for de-bond
3. Patient must have at least one, active white spot lesion identified by the Calcivis System immediately post de-bond
4. Patient and / or parent or guardian must be willing and able to give written informed consent
5. Patient and / or parent or guardian must be willing and able to adhere to study schedule

Exclusion criteria

1. Any Patient with recent tooth bleaching (within previous two weeks of imaging with the Calcivis System or within the follow-up period)
2. Any patient currently taking part in a clinical research study, or has taken part in a clinical research study in the previous three months
3. Pregnant and / or nursing mothers

8. STUDY PROCEDURES

8.1 Screening Procedures

Patients attending routine Orthodontic appointments to have their appliances checked, and who are identified by the Investigator as meeting the Inclusion and Exclusion criteria, and are ready for de-bond, will be approached to discuss their possible participation in the study.

Initial approach will be made by the Dental Nurse to ask the patient and / or parent or guardian, if they would be interested in participating in the study. The study will be explained to them and each patient and / or parent or guardian will be given a copy / copies of the Patient Information Sheet and Consent Forms to take away to read and discuss with others if required. Patients and / or parent or guardian will be asked to confirm their interest in participating in the study by contacting the Orthodontic clinic no less than 24 hours after being given the Patient Information and Consent Form. They will be given the opportunity to discuss their participation in the study and to ask the Investigator any questions. If the patient and / or parent or guardian is still willing for the patient to participate in the study, they will be asked to return to the Orthodontic clinic for Study Visit 1 (baseline), when written Informed Consent will be taken by the Investigator. Patient availability for the follow-up visits at 4 weeks (+/- 3 days) and 8 weeks (+/- 5 days) will also be checked.

The Site will document all patients and / or parents or guardians provided with the Patient Information Sheets, those attending Visit 1 baseline Visit and the outcome on a Patient Identification / Recruitment Log.

8.2 Study Visit 1 – de-bond - baseline

At this visit, written Informed Consent (ref. 15.3) will be taken by the Investigator and the following information collected and procedures carried out.

Pre-Imaging Information collected

Demographics – DoB and gender

Relevant medications – calcium supplements and antacids

Oral hygiene information – routine brushing regime, toothpaste and any other dental products used

Orthodontic history – date braces applied, type of bracket, ligation used, and any other relevant information (e.g. re-mineralization products used)

Preparation of the Calcivis System

The Calcivis System must be prepared according to the manufacturer's Instructions For Use. Single-use Disclosing Solution (Photoprotein) should not be reconstituted more than 2 hours before the first tooth is imaged. Once reconstituted, the multi-use vial of Disclosing Solution (Photoprotein) should be stored at 2 to 8^o, up to a maximum of 2 weeks.

Teeth Preparation Procedure

Immediately after the appliances have been removed, up to a maximum of four teeth from any of the four upper incisors and two canines with visible white spot lesions on de-bond, will be identified and recorded for assessment using the Calcivis System.

Each free smooth surface will be air dried before taking close-up colour photographs of the tooth or teeth with a digital camera for reference, and coded for ICDAS (1,2 or 3).

All relevant teeth will then be cleaned by the Orthodontist, by brushing with water, and rinsing with water and an air-water spray from a conventional dental 3-in-1 device, according to the Tooth Cleaning Protocol (Appendix 2). Patients will be asked to rinse out thoroughly with tap water.

Imaging with the Calcivis device

Extreme care must be taken to ensure the surface of the tooth and surrounding area are free from saliva before imaging with the Calcivis System by air drying for a minimum of 10 seconds immediately before application of the disclosing solution and Calcivis System imaging.

Images of the free smooth tooth surfaces, will be taken with the Calcivis System according the Instructions For Use. If the first image of a selected tooth is not clear, it is acceptable to take a second image of the selected tooth, however patients must rinse out with water before the subsequent image

can be taken, and the tooth air-dried as described above. A maximum of four images per patient can be taken with the Calcivis System.

Immediately after all imaging has been completed, patients will be asked to rinse out with tap water.

Any adverse events observed or volunteered by the patient will be recorded.

The images generated with the Calcivis System will be stored digitally on the laptop provided. The software overlays the two sets of images (before and after application of the disclosing solution), resulting in a demineralization map of each imaged tooth.

At the end of the imaging procedures, the Investigator will review the images on the laptop and record any 'activity' as a YES or NO, according to areas of elevated bioluminescence. If there is no area of elevated bioluminescence on a selected tooth surface, that tooth will not be followed up at future visits. Only patients with at least one tooth surface showing areas of active demineralization will be followed up.

In the event that none of the teeth imaged from a patient show any active demineralization, that patient will be withdrawn from the study and will be replaced.

At the end of Visit 1, the Investigator will share the images of the teeth with the patient and discuss the results.

The Calcivis System will be dismantled and cleaned according to the Instructions For Use and all consumables will be disposed according to the Instructions For Use.

Representatives of the Sponsor, Calcivis Ltd, will be available throughout Visit 1 and any subsequent visits, to provide technical support for the use of the Calcivis System, as and when required. Consent will be sought from the patient and / or parent or guardian.

Patients will then resume routine procedures carried out at de-bond. Patients will be advised to follow a routine tooth brushing / oral hygiene regime of brushing teeth at least twice per day with a fluoride toothpaste, taking care to brush any areas highlighted by the orthodontist, and to use a mouthwash at different times of the day from brushing.

Post-Imaging Questionnaires

At the end of the imaging procedures, patients will be asked to remain at the Orthodontic clinic to complete a Patient Questionnaire. Visit 1 is then complete.

In addition, at the end of each baseline study visit, the Investigator and Dental Nurse will each complete relevant sections of a User-Questionnaire

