4. STUDY OBJECTIVES AND ENDPOINTS

4.1 Primary Objective

Primary Objective - to assess the Calcivis System for monitoring the activity levels of post-orthodontic treatment white spot lesions as an indicator of either 1) gradual arrest of lesion activity (remineralisation / repair) or 2) continuing lesion activity (on-going demineralisation) of the Calcivis System –

this will be measured by bioluminescent output over time from baseline (de-bond) to 8 weeks post be-bond (presence or absence of bioluminescence)

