5.2 General Description

The Calcivis Caries Activity Imaging System comprises:

Calcivis Imaging Kit - Administration and Imaging device

[figure not shown]
Consists of:

- Calcivis Intra-oral Imaging Device
- Device cradle
- Calcivis (Imaging) Software on DVD/CD
- Calcivis Instruction Manual

The software main functions are; to initiate imaging (visible and luminescent), to save and retrieve digital images for display, and the overlaying of black and white images with luminescence images to map location of luminescence, representing elevated calcium levels, to the tooth surface.

The software requirements are detailed in the Instructions For Use.

Figure 2: Calcivis Intra-oral Imaging Device

Accessory - Calcivis Disclosing Solution Kit – single-use

Consists of:

- Calcivis Disclosing Solution (Freeze-dried in vials)
- Ampoules of Water for reconstitution
- Ampoule Snapper
- Syringe
- Needleless adaptor (for reconstitution only)

and / or

Accessory – Calcivis Disclosing Solution (Photoprotein) Kit - multi-use

Consists of:

- Calcivis Photoprotein (Disclosing Solution) - Freeze dried in a vial
- Vial of Calcivis Diluent (water for reconstitution)
- Single-use Device Syringes (sterile prior to opening)
- Vial Adaptors x 2

Accessory – Calcivis Application Kit

Consists of:

- Single-use Calcivis Applicators x10

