In May 2014, the first formal Post-Approval Clinical Study was performed in adults (16 to 25 yrs old) using the advanced prototype Calcivis System. The Primary Objectives of the study were to assess the Performance and Safety of the Calcivis System, and the Secondary Objective was to assess user experience with the Calcivis System (both User and Patient). A total of 42 patients were recruited to the study from three UK, General Dental Practices, to obtain a total of 31 evaluable patients. Eligible patients were those with interpretable images of both a tooth with no visible lesion identified (ICDAS Code 0) and a tooth with a suspected visible lesion identified (ICDAS Code 1, 2 or 3). Images from 11 patients were not eligible for interpretation due to confounding factors including ambient light ingress, gross saliva contamination and poor disclosing solution coverage on the tooth surface. All these issues have been addressed in the design phase for the new commercial Calcivis System which is the subject of this study.

All 42 patients were included in the Safety Population – two adverse events were recorded – bleeding gums and slight gum abrasion – both were device-related, non-serious and asymptomatic to the patients with no action required. One other adverse event was recorded as a device deficiency when the device jammed and did not dispense fluid.

31 patients were included in the Agreement Population – analysis of the level of agreement between the ICDAS scores and elevated luminescence, (Y/N) as defined by the Investigators.

For the primary study objectives, the study results concluded that: -

1. The Calcivis System was safe in clinical use as determined by the low number and minor nature of the adverse events recorded.
2. Analysis of the overall level of agreement between elevated luminescence and the presence of lesions predicated as active by the Investigators showed agreement in 47 of the 65 teeth imaged (72.3 %) which was statistically significant, not due to chance and above the expected level of 70%.

(Of the 31 teeth identified by the Investigators with no visible lesions, 26 showed no elevated luminescence using the Calcivis System – corresponding to a negative percentage agreement of 83.9%. Of the 34 teeth with visible lesions identified by the Investigators, 21 showed elevated luminescence using the Calcivis System – corresponding to a positive percentage agreement of 61.8%).

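### The objective is about the white spot lesion, but the follow-up rule and the YES/NO readings are worded for the tooth surface, with no requirement that the light lie on the lesion

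*Protocol*

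**What the plan says.** Several places in the protocol take the lesion as the unit.

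- Section 4.1 sets out "to assess the Calcivis System for monitoring the activity levels of post-orthodontic treatment white spot lesions", with arrest and continuing activity as the two possible findings.
- Inclusion criterion 3 in section 7.4 reads: "Patient must have at least one, active white spot lesion identified by the Calcivis System immediately post de-bond".
- Section 5.3 says that in this study the device is applied to a specific site where a possible lesion has already been found.
- The synopsis (follow-up entry) and section 7.2 also speak of lesions judged active or inactive.

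The working rules take the tooth surface as the unit.

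- Section 8.2, on the tooth: "If there is no area of elevated bioluminescence on a selected tooth surface, that tooth will not be followed up at future visits".
- Section 8.2, on the patient: "Only patients with at least one tooth surface showing areas of active demineralization will be followed up".
- Sections 8.2, 8.3 and 8.4 each have the Investigator record activity as YES or NO from regions of raised luminescence. They do not mention the white spot or the region that was lit at Visit 1.
- Section 10.2 summarises the percentage of teeth that luminesce.

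The measure in section 4.1 names no location either: "this will be measured by bioluminescent output over time from baseline (de-bond) to 8 weeks post be-bond (presence or absence of bioluminescence". Yet the location is available, because section 5.2 says the software overlays the two images "to map location of luminescence, representing elevated calcium levels, to the tooth surface".

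**The concern.** The study expects white spots beside brackets to pass from active to inactive within weeks of de-bond (section 3.4). The reading that matters is therefore whether a given lesion, lit at baseline, is still lit at 8 weeks. A surface-level YES/NO answers a different question. If the lesion has gone dark but another part of the same surface glows at Visit 3, the tooth is recorded as YES, and the objective interprets YES as continuing lesion activity. For a lesion that was lit at baseline, this error runs only one way: it hides arrest.

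The protocol gives a reason to expect some such light. Section 5.6 notes that raised calcium can also come from erosion, fluorosis or hypomineralisation.

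This is a data-capture rule, so an analysis plan cannot repair it. One YES/NO per tooth cannot be split by location later without going back to the images, and the protocol plans no such re-read for analysis.

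**Working it through.** **Step 1. Compare the units.**

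| Element | Where | Unit |
|---|---|---|
| Primary objective | 4.1 | white spot lesion |
| Inclusion criterion 3 | 7.4 | white spot lesion |
| Use of device in this study | 5.3 | specific lesion site |
| Choice of teeth to image | 8.2 | tooth with a visible white spot |
| Rule for following a tooth | 8.2 | tooth surface |
| Visit 1 to 3 reading | 8.2, 8.3, 8.4 | one YES/NO, no location |
| Summary | 10.2 | tooth |

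The unit moves from lesion to surface at the point where data are recorded, and it does not move back.

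**Step 2. Reproduce the protocol's figures.** Section 5.7 reports the earlier prototype study.

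- Negative agreement: of 31 teeth without a visible lesion, "26 showed no elevated luminescence using the Calcivis System". 26/31 = 83.9%, as stated.
- Positive agreement: 21/34 = 61.8%, as stated.
- Overall: (26 + 21)/65 = 72.3%, as stated.

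**Step 3. Derive a proxy for off-lesion light.** Luminescence on teeth without a visible lesion: 31 − 26 = 5, and f = 5/31 = 16.1%. The exact (Clopper-Pearson) 95% interval is 5.5% to 33.7%.

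**Step 4. Illustrate the effect on recorded arrest.** Take teeth whose white spot was lit at baseline. Let a be the true proportion of those lesions dark at Visit 3. Assume off-lesion light occurs with probability f, independently of the lesion. A tooth reads NO only if the lesion is dark and there is no light elsewhere:

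recorded NO = a × (1 − f)

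The protocol gives no value for a, so these are assumptions:

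| Assumed true arrest a | f = 5.5% | f = 16.1% | f = 33.7% |
|---|---|---|---|
| 50% | 47.3% | 41.9% | 33.1% |
| 70% | 66.2% | 58.7% | 46.4% |
| 90% | 85.1% | 75.5% | 59.6% |

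For example, 0.70 × (1 − 0.161) = 0.587, a shortfall of 11.3 percentage points. Whatever the value of a, the relative shortfall equals f.

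**The case against.** The strongest reply is that the protocol does frame the assessment by lesion. Criterion 3, section 5.3, section 7.2 and the synopsis all speak of lesions, and only teeth with a visible white spot are imaged. A trained Investigator may well look only at the lesion. Image interpretation is a training item (sections 5.10 and 14.7), and the Instructions For Use, which are not shown, could contain a reading convention. This stands as far as it goes. It means that practice may be better than the text, but the text does not require it and the reading does not show which approach was used. Section 7.1 provides for three Investigators, so their approaches could differ unnoticed.

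A reader might infer three stronger claims that the document does not support.

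- *That light anywhere on the surface is declared to count as an active lesion.* No section says so. It follows only from the absence of a location rule.
- *That section 8.2 admits patients who fail criterion 3.* The two follow-up sentences state necessary conditions, not sufficient ones. Criterion 3 is applied per patient and remains in force.
- *That location is lost.* The overlay images are stored, and reference photographs are taken at every visit, so a re-read by lesion is possible.

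The figures are also open to challenge. The 5/31 is a whole-tooth rate from an advanced prototype used in general dental practices. Section 5.7 describes the teeth in that study by occlusal eruption stage, whereas this study images the smooth surfaces of upper incisors and canines. Section 3.3 adds that some teeth judged sound may have had sub-clinical active lesions. The figure does not measure off-lesion light in this population.

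Finally, the study is descriptive and unpowered, and a tooth-level summary is a coherent thing to report. But a descriptive percentage still has to describe the lesion that the objective names.

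**Conclusion.** The point holds as a mismatch between the objective and the recorded reading. The objective, criterion 3 and the site-specific use of the device concern the lesion. The follow-up rule is worded for the surface, and the readings carry no requirement that the light lie on the identified lesion or at the baseline site. Read as written, this understates arrest among lesions lit at baseline.

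The size is unknown. The fall from 70% to about 59% (about 46% to 66%) rests on an assumed arrest rate, a borrowed off-lesion rate and independence. It shows only that the effect need not be negligible. The conclusion rests on the wording and would stand without the figures.

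**What to change.** - **Sections 8.2 to 8.4, reading.** Chart each white spot lesion at Visit 1 on the device's own visible image, taken after cleaning, with the reference photograph as support. At Visit 1 that photograph precedes cleaning, so it should not be the only anchor. Record YES/NO for elevated luminescence on the charted lesion, and use the same site at Visits 2 and 3. State in the reading instruction what counts as light on the lesion.
- **Separate box.** At each visit, record whether there is luminescence elsewhere on the surface.
- **Section 8.2, follow-up rule.** Reconcile its wording with inclusion criterion 3, so that both refer to the lesion.
- **Sections 4.1 and 10.2.** Use the lesion-site reading for the primary objective. Tabulate the off-lesion and any-surface readings separately, so the tooth-level summary is still available.

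Cost: slightly more reading time per image, a revised reading form and a short addition to training. Slightly fewer teeth may count as active at baseline. No extra imaging is needed, since overlays and photographs are already taken at every visit. For patients already imaged, the stored images allow the lesion-site reading to be made retrospectively.
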